The Effectiveness of TECH: Tablet Enhancement of Cognition and Health

NCT02955277

March 2020

OBJECTIVES

To establish the effectiveness of the ‘Tablet Enhancement of Cognition and Health’ (TECH), a novel cognitive intervention for improving global cognition, specific cognitive components, and health-related quality of life (HRQoL) in older adults with Mild Cognitive Impairment (MCI), compared with a control group.

METHODS

Study design

This is a single-blind randomized controlled trial (clinical trial number NCT02955277) with assessments administered pre and post the 5-week intervention, and at 6-month follow-up, by assessors blind to group allocation.

Population

Community dwelling older adults (>65 years) were recruited from two community geriatric clinics due to their memory problems, and were referred to the study by their family or geriatric physician. Inclusion criteria were as follows: a) a diagnosis of MCI, as determined by a score of 19-25 points on the Montreal Cognitive Assessment (MoCA), a valid and reliable tool, subjective memory complaints supported by a family member, and independence in basic and instrumental activities of daily living (BADL, IAD), b) normal or corrected vision and hearing, c) written and spoken fluency of the language, and d) ability to use a touchscreen tablet after an initial demonstration. Individuals were excluded if they experienced severe depressive symptoms (Geriatric Depression Scale > 10 points), and if they were diagnosed with dementia, or other neurological or psychiatric conditions. All participants signed informed consent forms before participating in the study.

Tools

Outcome measures

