The **Primary outcome measure** was MoCA (Nasreddine et al., 2005), for assessing global cognition, which was also used to screen for eligibility. **Additional cognitive assessment** included the WebNeuro assessment (Silverstein et al., 2007) which is A valid computerized assessment battery including the assessments of the following specific cognitive components/domain (subtests): Sustained attention (Continuous Performance Task), 22 controlled attention (Verbal Interference Task), flexibility (Switching of Attention Task), inhibition (Go-NoGo Task), working memory (Digit Span Task), memory recall (Memory Recall Task), problem solving (Maze Task). For each domain a raw score was calculated, and then converted to a z score, with a normative average of 0, and a standard deviation of 1. Higher scores for each domain indicates better performance. The secondary outcome measures included The Tower of Hanoi (ToH) task (Simon, 1975), a commonly used goal-directed measure assessing problem-solving, and specifically, planning. A computerized version of the task was used (<http://vornlocher.de/tower>). The participants completed the first three (out of six) levels of the task. the number of moves per level, and time for completion were recorded. the 12-Item Short Form Health Survey (SF-12) (Ware, Snow, Koskinski, & Gandek, 1993) for measuring health-related quality of life; physical and mental composite summary scores (Wilson, Tucker, & Chittleborough, 2002), higher scores indicating better health measures (Ware et al., 1993). The General Self-Efficacy Scale (GSES) (Schwarzer& Jerusalem, 1995), which is highly reliable and valid scale for assessing optimistic self-beliefs to cope with a variety of difficult demands in life. It consists 10 statements such as

'I can solve most problems if I invest the necessary effort'. The total score ranges from 10 to 40. Higher scores represent higher levels of general self efficacy (Schwarzer & Jerusalem, 1995). In addition, demographic information and previous experience with technology use (computer, smartphone and tablet) were collected.

The Intervention

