The TECH intervention (study group) included daily self-training facilitated by weekly group sessions. Participants received iPads to take home and were requested to play puzzle-game apps, which simultaneously provided practicing different cognitive components, 3-5 times a week X 30-60 minutes, for a total of 15-25 training sessions. Weekly one-hour sessions led by an occupational therapist (OT) took place in a small group setting (4-6 participants) over a five-week period. These sessions focused on teaching tablet operation, allowing participants to explore and practice new apps, and increasing their confidence and independence in using and activating the tablet.

Standard care (control group). Participants received standard occupational therapy care for MCI including either a) a single consultation in a group setting (4-6 participants) to encourage participants to engage in activities such as solving crossword puzzles or playing board or card games in their leisure time to stimulate cognitive function; or b) participation in a social group (six one-hour sessions of 4-6 participants) of playing puzzle board games, with no recommendation to perform self-training at home.

Procedure

Participants were approached by phone and were provided with information about the study. Those who were willing to participate were invited to the geriatric clinic for the assessment session. After signing an informed consent form, the MoCA, GDS, BADL,

and IADL questionnaires were administered to confirm eligibility. If the participants were found eligible, the remaining outcome measures were administered. Then participants were stratified according to low (19-22 points) or high (23-25 points) MoCA score and then randomly allocated to the TECH or control group using a 1:1 ratio. Allocation was concealed from the investigators and the enrolled participants. Participants were notified by phone about their allocation. The assessors, who were blind to group allocation, were OTs trained to assess the study. Participants who were invited to the post- and follow-up assessment sessions were asked not to discuss the intervention with the assessors.

Data analysis

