'IBM SPSS Statistics 25' software was used for descriptive statistics to characterize the sample and outcome measures for the three assessments. Since the outcome measures were not normally distributed, non-parametric tests were performed. Intention-to-treat analysis was conducted with the last observation carried forward method, which is an acceptable data imputation method.²⁶ The percentage change was calculated for MoCA, WebNeuro, and SF-12 measurements between pre and post and between pre and follow-up using these formulas[(post-pre)/pre*100%], [(follow-up-pre)/pre*100%]. The difference between groups for the percentage change was tested using the Mann Whitney Test. Since significance tests are highly dependent on the sample size, the effect size was also estimated by using the effect size formula for non-parametric tests: Cohen's $r=Z/\sqrt{N}$. The Z value was retrieved from the Mann Whitney test U output. Cohen's r effect size values were considered small (0.1), medium (0.3), and large (0.5).

In each group, we calculated the percentage of participants who achieved the Minimal Clinically Important Difference (MCID) improvement in global cognition. MCID is defined as the smallest change in scores perceived by the patient as beneficial, which could lead to a change in the patient's treatment. In this study, the MCID of the MoCA was considered an improvement of at least 1.22 points, as found in Stroke Rehabilitation (since MCID data for individuals with MCI, to the best of our knowledge, have not yet been established).

The sample size was calculated using 'G*Power 3.1.9.4' software, according to a small effect size, based on previous studies assessing the effectiveness of computerized cognitive training for older adults with MCI, with 80% power and a significance level of 0.05. A sample size of 68 participants was calculated. Taking into consideration a 20% drop-out rate, 80 participants were required.

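### Percentage change is taken on WebNeuro z scores centred on 0, so improvement from a negative baseline counts as decline and the domain comparisons can miss or reverse a real effect

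*Combined protocol and SAP*

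**What the plan says.** Under Outcome measures, the raw score of each of the seven WebNeuro domains is "converted to a z score, with a normative average of 0, and a standard deviation of 1". The direction is also given: "Higher scores for each domain indicates better performance".

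The Data analysis section then states: "The percentage change was calculated for MoCA, WebNeuro, and SF-12 measurements between pre and post", and likewise for pre to follow-up, "using these formulas[(post-pre)/pre*100%], [(follow-up-pre)/pre*100" (the closing percent sign and bracket follow in the text). The denominator is the signed baseline score. The treatment comparison is made on this quantity: "The difference between groups for the percentage change was tested using the Mann Whitney Test". The effect size is r = Z/√N, and "The Z value was retrieved from the Mann Whitney test U output".

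The plan describes no absolute value in the denominator, no rescaling, no rule for baselines at or near 0, and no return to raw scores for WebNeuro.

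**The concern.** A percentage change needs a scale with a true zero and positive values. A z score has neither: 0 is simply the normative average, and about half of a normative sample lies below it. On such a scale the formula does three things:

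- It reverses the direction of change for everyone with a negative baseline.
- It gives very large values for baselines close to 0.
- It has no value at 0.

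The population makes negative baselines plausible. The protocol says: "Community dwelling older adults (>65 years) were recruited from two community geriatric clinics due to their memory problems", and all had MCI. It gives no WebNeuro baseline values, so their frequency is not known.

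Improving specific cognitive components is part of the stated objective, and WebNeuro is the battery that measures them by domain. Seven domains at two intervals give 7 × 2 = 14 between-group comparisons. If TECH helps, these can show nothing or show harm; if TECH harms, they can show benefit.

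**Working it through.** **Inputs from the documents.** Domain score: z, normative mean 0, SD 1, higher better (Outcome measures). Formula: (post − pre)/pre × 100% (Data analysis). Test: Mann-Whitney on that percentage, with r from the same Z (Data analysis). Size: 68 before drop-out and 80 after (Data analysis), with participants "randomly allocated to the TECH or control group using a 1:1 ratio" (Procedure), so 34 or 40 per arm. The plan gives no figure of its own for the WebNeuro comparison, so there is none to reproduce.

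**Step 1: direct evaluation of the formula.**

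| pre | post | true change (SD) | planned percentage |
|---|---|---|---|
| −1.0 | −0.5 | +0.5 | (0.5)/(−1.0) = −50% |
| −0.5 | −1.0 | −0.5 | (−0.5)/(−0.5) = +100% |
| −2.0 | −1.5 | +0.5 | (0.5)/(−2.0) = −25% |
| 0.5 | 1.0 | +0.5 | (0.5)/(0.5) = +100% |
| 0.05 | 0.55 | +0.5 | (0.5)/(0.05) = +1000% |
| −0.05 | 0.45 | +0.5 | (0.5)/(−0.05) = −1000% |
| 0 | 0.5 | +0.5 | undefined |

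In general, a benefit of d added to the post score moves the percentage by 100·d/pre, which is negative whenever pre is negative.

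**Step 2: how many participants are affected.** If baseline z is normal with mean μ and SD 1 (assumed), the share with a negative baseline is Φ(−μ): 50% at μ = 0, 69% at −0.5, 84% at −1, 93% at −1.5 and 98% at −2. The share within 0.1 of zero falls from 8% at μ = 0 to 1% at μ = −2.

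**Step 3: effect on the test.** Assume post = μ + ρ(pre − μ) + √(1 − ρ²)·e + d, with e standard normal and d = 0 in the control arm. At μ = 0, (post − pre)/pre = (ρ − 1) + (√(1 − ρ²)·e + d)/pre. Since pre is symmetric about 0, this is symmetric about ρ − 1 in both arms whatever d is. A percentage from TECH then exceeds one from control with probability ½, so the Mann-Whitney test has no shift to detect. For μ below 0, reversed participants are the majority and the apparent effect points the wrong way.

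Simulation: 34 per arm, ρ = 0.7, d = 0.5 SD, two-sided 0.05, 2000 trials per row. Entries are percentages of trials with a significant result.

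| Baseline mean μ | Absolute change favours TECH | Percentage change favours TECH | Percentage change favours control |
|---|---|---|---|
| +1 | 71.9 | 30.0 | 0.0 |
| 0 | 73.1 | 2.2 | 1.8 |
| −0.5 | 72.3 | 0.3 | 11.4 |
| −1 | 72.2 | 0.0 | 30.4 |
| −1.5 | 72.4 | 0.0 | 52.9 |
| −2 | 72.6 | 0.0 | 65.1 |

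**Step 4: sensitivity to the assumptions.**

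- *40 per arm, ρ = 0.6, d = 0.5.* Absolute change detects the benefit in about 67% of trials. Across three separate runs at μ = 0, −0.5 and −1, percentage change detects it in 2-3%, 0.2-0.7% and 0-0.1%, and significantly favours control in about 2%, 10-12% and 29-30%. At μ = +0.5 and +1 it detects 11-12% and 27-28%.
- *34 per arm, ρ = 0.7, d = 0.2, μ from 0 to −2.* Absolute change favours TECH in 16-18%. Percentage change favours TECH in 0.2-2.2% and control in 2-15%.
- *34 per arm, ρ = 0.7, d = 0.8, μ = −1.* Absolute change favours TECH in 99%; percentage change favours control in 62%.
- *34 per arm, ρ = 0.7, d = 0.* Percentage change rejects in 4.6-6.4% of trials in total, around the nominal 5%.

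**The case against.** The strongest objection is textual. The Data analysis section says only that percentage change was calculated for WebNeuro; it does not say whether the raw or the z score entered the formula. With raw scores, the reversal caused by a zero-centred scale would disappear. This stands as a reason to ask the sponsor. It does not remove the concern: the z score is the final domain score described, it carries the statement of direction, and no other WebNeuro scale is named for analysis. The documents do not describe the raw metrics, so nothing firm can be said about percentage change on them.

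Second, the test keeps its size when treatment has no effect, because the arms are randomised. That is correct: the damage is to direction, power and r, not to the false-positive rate. Likewise, a huge ratio takes only an extreme rank in a Mann-Whitney test, so reversal does most of the harm.

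Third, the simulation settings are assumed: baseline mean, SD, normality, correlation and effect. The plan itself says the outcomes were not normally distributed and that the sample size was based on a small effect, and last observation carried forward was not modelled. The chance of significant harm does depend on these settings. At μ = +1 no reversal was seen, and at 0.2 SD it is much rarer than at 0.5 SD. Yet at every baseline mean tried, power for a 0.5 SD benefit was less than half that of absolute change, and the arithmetic in Step 1 needs no distribution.

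Fourth, WebNeuro is an additional assessment and MoCA is primary. MoCA baselines are 19-25 by eligibility, so its sign cannot flip, and the MCID analysis uses points. This limits the scope of the concern but does not answer it.

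**Conclusion.** The concern holds. Read together, the two sections apply a signed ratio to a scale centred on 0, and nothing else in the document repairs it. The change of every participant with a negative baseline is scored in the wrong direction.

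For a true benefit of 0.5 SD, the chance of a significant result favouring TECH falls from 72-73% with absolute change to 2.2% at a baseline mean of 0 and essentially nil at −1, where 30% of trials significantly favour control (34 per arm, ρ = 0.7). Even at a mean of +1 it is only 30%. These rates rest on the assumed values stated above; the reversal itself rests only on the document's formula and score definition. It also presumes that z scores were the values analysed, which is the natural reading.

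The 14 WebNeuro comparisons and their r values should not be interpreted as written. The MoCA comparison is not affected by this fault.

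**What to change.** 1. State which WebNeuro score entered the formula.
2. If it was the z score, drop percentage change for all seven domains. Either apply the Mann-Whitney test to the absolute change in z (post − pre and follow-up − pre), or compare the later z between arms adjusted for baseline z by ANCOVA or rank ANCOVA. The first is the smallest change to the plan; either removes the fault.
3. Recompute the effect size from the new analysis: r from the new Z where the Mann-Whitney test is kept.
4. Do not merely put |pre| in the denominator. That restores direction (66-71% favouring TECH at baseline means 0 to −2 for 0.5 SD, 34 per arm), but the ratio still has no meaning on a z scale and is undefined at 0.

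The cost is one rewritten sentence in the plan and a re-run of 14 tests on data already collected. The document reports the analysis in the past tense, so the change should be labelled post hoc and the percentage-change results shown alongside.

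### MoCA, the sole primary outcome, is compared between arms at two visits with no primary visit, hierarchy or adjustment; if either visit can count as success, the false-positive risk in either direction is up to 9.75%

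*Combined protocol and SAP*

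**What the plan says.** The Outcome measures section names MoCA as the primary outcome, "for assessing global cognition, which was also used to screen for eligibility", and attaches no time point to it. Under Study design the trial is described "with assessments administered pre and post the 5-week intervention, and at 6-month follow-up". The Objectives speak of improving global cognition and do not say when.

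The Data analysis section calculates percentage change in MoCA "between pre and post and between pre and follow-up", with one formula for each, and continues: "The difference between groups for the percentage change was tested using the Mann Whitney Test". The two comparisons are written in parallel. Neither is called primary, no order of testing or adjustment is given, and nothing says what the trial concludes if they disagree.

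The only significance level is in the sample-size paragraph: "with 80% power and a significance level of 0.05". It is not said to be one- or two-sided, and it is not described as an error rate for the trial as a whole. The same section also reports the percentage of participants in each group who reach a minimal important difference on MoCA, but names no test for it, so it is not counted here.

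**The concern.** A single primary outcome normally means one test and one chance of a false positive. Here one outcome is tested twice. If each test is run at the only level the document gives, there are two routes to a positive primary result. A post-only effect, a follow-up-only effect, or both could each be presented as meeting the objective.

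Two things are at stake. The error rate of the primary conclusion may exceed the level used to size the trial. And if the visits disagree, the plan gives no basis for saying whether the trial succeeded.

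**Working it through.** **Inputs from the document.** Two MoCA comparisons; Mann-Whitney test on percentage change; level 0.05; 1:1 allocation; 80 participants (40 per arm); missing values filled by last observation carried forward (LOCF).

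**Assumptions, because the document is silent.** Each test is two-sided at 0.05 (one-sided also shown). Significance at either visit counts as success. The correlation ρ between the two test statistics is varied from 0 to 0.9.

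**The plan's own figures.** One two-sided test at 0.05 has a 5% chance of a false positive, of which 2.5% favours TECH. The sample size of 68 does not help to identify a primary visit. It does not follow from the stated inputs (on the document's own scale a small effect is r = 0.1, or d about 0.2, which needs 786 in total for a two-sided comparison of two means). That is a separate matter.

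**Two tests, independent.** 1 − 0.95² = 0.0975, or 9.75%. Favouring TECH only: 1 − 0.975² = 0.0494, or 4.9%.

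**Two tests, correlated.** With (Z₁, Z₂) bivariate normal under no effect:

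- either direction: 1 − P(|Z₁| < 1.96 and |Z₂| < 1.96)
- favouring TECH: 1 − P(Z₁ < 1.96 and Z₂ < 1.96)
- one-sided 0.05 tests: 1 − P(Z₁ < 1.645 and Z₂ < 1.645)

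| ρ | Two-sided, either direction | Two-sided, favouring TECH | One-sided 0.05 each |
|---|---|---|---|
| 0 | 9.75% | 4.9% | 9.75% |
| 0.3 | 9.5% | 4.8% | 9.3% |
| 0.5 | 9.1% | 4.5% | 8.8% |
| 0.7 | 8.35% | 4.2% | 8.0% |
| 0.8 | 7.8% | 3.9% | 7.5% |
| 0.9 | 7.0% | 3.5% | 6.8% |
| One test only | 5% | 2.5% | 5% |

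**Where ρ might lie.** Both changes share the baseline. If the three scores have equal variance σ² and equal pairwise correlation c, the two changes have covariance σ²(1 − c) and variance 2σ²(1 − c) each, so ρ = 0.5. If LOCF copies the post value into follow-up for 20% of participants, ρ becomes about 0.8 × 0.5 + 0.2 × 1 = 0.6. Closer agreement between the two later visits would raise it further.

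**Check by simulation.** Null trials were simulated with 40 per arm, rounded scores, percentage change and Mann-Whitney tests (8,000 per scenario, so a Monte Carlo standard error of about √(0.09 × 0.91/8000) = 0.3 percentage points). Each single test rejected in 4.4-5.3% of trials. At least one rejected in 9.6% with no drop-out (correlation of changes 0.51), and in 7.1-9.1% across LOCF scenarios (correlations 0.56 to 0.84). Rejection favouring TECH occurred in 4.8% and 3.8-4.4% respectively. This agrees with the table.

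**After the fix.** In a fixed sequence, follow-up is tested only after a significant post comparison. If there is no effect at either visit, a false positive requires the first test to reject, so the chance is 5%. With Bonferroni at 0.025 per visit it is 1 − 0.975² = 4.9% if independent, 4.65% at ρ = 0.5 and 4.0% at ρ = 0.8.

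**The case against.** The strongest reply is that the plan contains no rule that either visit is enough. Treating post-intervention as primary by convention, or requiring both visits, fits the text equally well, and neither would inflate the error. The 0.05 belongs to the sample-size calculation, so no declared trial-wide rate is being breached. This stands: the inflation depends on a reading that the plan permits but does not state. It does not remove the point, because nothing in the document excludes that reading.

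A reader might also infer that the chance of a false claim of effectiveness is 8-10%. The documents do not support that. For two-sided tests that range includes results in which TECH is significantly worse; the share favouring TECH is about half and stays below 5%. The range would describe false claims of benefit only if the tests were one-sided at 0.05, which is not stated. Its lower end also needs a correlation of at most about 0.75, and the documents give none.

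Finally, the section is written in the past tense and reports that the outcomes had already been found to be non-normal. If results by arm had been seen, naming a primary visit now would be a post hoc choice and would not restore error control. This stands as well, and the fix has to allow for it.

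**Conclusion.** The concern holds in a conditional form. The document fully specifies two tests of its one primary outcome and gives no primary visit, hierarchy, adjustment or success rule. If either visit counts and both tests are two-sided at 0.05, the false-positive risk in either direction is at most 9.75% for positively correlated tests, and about 7-9.5% for assumed correlations of 0.9 down to 0.3. The risk of a false result favouring TECH is about 3.5-4.9% against 2.5%, an increase of roughly 1.4 to 2 times (3.5/2.5 = 1.4; 4.9/2.5 = 1.96).

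The correlation, the sidedness and the either-visit rule are all assumptions. The document does not show that the sponsor intended to claim success on either visit, nor that a promised 5% trial-wide rate was broken. What it does show is that the primary conclusion is undefined when the visits disagree.

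**What to change.** **If MoCA results by arm had not been seen.** State in the Data analysis section that the between-arm MoCA comparison at the post-intervention visit is the single primary test, at two-sided 0.05. State that the 6-month comparison is tested at 0.05 only if the first is significant, as a key secondary test of durability. Tie the power statement to the post-intervention comparison. This takes a sentence or two and costs the post-intervention test no power. The small downside is that an effect seen only at follow-up could no longer be claimed as confirmatory.

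If the sponsor wants either visit to be able to carry the claim, testing each at 0.025 is the alternative. It raises the required sample by about 21%: 68 × 1.21 = 82.3, or 84 evaluable after rounding up to 42 per arm.

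**If MoCA results by arm had already been seen.** Do not select a visit. Report both comparisons with equal prominence and Holm- or Bonferroni-adjusted p-values, which keep the error at or below 5% whatever the correlation, and disclose that no primary time point was prespecified. This needs no new data, but a result that is only just below 0.05 at one visit may no longer be significant after adjustment.

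### The primary MoCA test uses neither the MoCA randomisation strata nor baseline MoCA as a covariate: no inflation of type I error, but a modest and avoidable loss of precision

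*Combined protocol and SAP*

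**What the plan says.** - **Design (Procedure).** Before 1:1 allocation, "participants were stratified according to low (19-22 points) or high (23-25 points) MoCA score". Blocking within strata is not described.
- **Baseline (Outcome measures).** MoCA is the primary outcome, "which was also used to screen for eligibility". Baseline MoCA should therefore exist for every randomised participant.
- **Test (Data analysis).** MoCA is converted to percentage change from pre to post and from pre to follow-up, and "The difference between groups for the percentage change was tested using the Mann Whitney Test". The only between-group effect measure is r = Z/√N. No stratum, covariate or adjusted sensitivity analysis is described.
- **Reason for ranks (Data analysis).** "Since the outcome measures were not normally distributed, non-parametric tests were performed".
- **Missing data (Data analysis).** "Intention-to-treat analysis was conducted with the last observation carried forward method".
- **Responders (Data analysis).** "In each group, we calculated the percentage of participants who achieved the Minimal Clinically Important Difference (MCID) improvement in global cognition". No between-group difference or interval is described for this proportion.

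**The concern.** The design treats baseline MoCA as prognostic, since it balances the arms on it. The analysis then uses baseline only inside the percentage formula, and this has two consequences.

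- An unstratified test computes its variance as if the strata had not been balanced, so it gives no credit for balance achieved.
- A change score fixes the pre-to-post slope at 1 instead of estimating it. If the true slope is β, Var(post − pre) = residual variance + (1 − β)² × Var(pre), and the second term is avoidable noise. Dividing by baseline adds another distortion: a gain of 2 points is 2/19 = 10.5% for someone starting at 19 but 2/25 = 8.0% for someone starting at 25, so equal gains receive different ranks.

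Eligibility selects on an imperfectly reliable screening score, so a slope below 1 is likely. At stake is some power on the primary outcome of a trial of about 80 people, together with an effect estimate in MoCA points, which r cannot provide.

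**Working it through.** **Inputs from the documents.** Baseline range 19-25; strata 19-22 and 23-25; 1:1 allocation; Mann-Whitney on percentage change; LOCF; significance level 0.05 (two-sided assumed); and "Taking into consideration a 20% drop-out rate, 80 participants were required". The plan has no figure of its own to reproduce on this point, and only N = 80 and the 20% drop-out are taken from its sample-size statement.

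**Assumed inputs.** True score normal with mean 22.5; independent pre and post errors; scores rounded, post capped at 30; baseline kept if 19-25; allocation balanced within strata; 1-point effect. LOCF gives each participant a 20% chance, at random, that post equals baseline.

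**Step 1: slopes.** Slope ≈ true variance/(true variance + error variance).

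- SDs 2.5/1.5: 6.25/8.50 = 0.74 (0.73 simulated)
- SDs 2/1.5: 4/6.25 = 0.64 (0.63 simulated)
- SDs 2.5/2: 6.25/10.25 = 0.61 (0.61 simulated)

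With 20% carrying baseline forward, slope ≈ 0.8β + 0.2: 0.78, 0.70 and 0.69 (simulated 0.78, 0.70, 0.68).

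**Step 2: type I error.** If strata are perfectly balanced and explain a share R² of the rank variance, size = 2[1 − Φ(1.96/√(1 − R²))]. R² = 0.035 gives 0.0460, and R² = 0.13 gives 0.0356. Simulation:

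| Setting | Planned test | Adjusted tests |
|---|---|---|
| N = 80, balanced strata, LOCF | 4.2-4.6% | 4.7-5.6% |
| N = 80, balanced strata, complete | 4.1-4.5% | 4.9-5.3% |
| N = 68, blocked strata, complete | 3.7-4.8% | 4.7-5.3% |
| N = 68, simple randomisation within strata, complete | 4.6-4.9% | 4.8-5.1% |

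**Step 3: power at N = 80, normal errors** (30,000 trials per setting; SE of each gain at most 0.22 points; gains computed before rounding).

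| True/error SD | Data | Planned | Gain, van Elteren on absolute change | Gain, rank ANCOVA |
|---|---|---|---|---|
| 2.5/1.5 | LOCF | 43.2% | +2.2 | +3.1 |
| 2/1.5 | LOCF | 42.9% | +3.2 | +4.5 |
| 2.5/2 | LOCF | 27.8% | +1.9 | +2.7 |
| 2.5/1.5 | complete | 53.4% | +3.0 | +3.3 |
| 2/1.5 | complete | 53.2% | +4.7 | +6.0 |
| 2.5/2 | complete | 35.3% | +2.9 | +3.9 |

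**Step 4: splitting the van Elteren gain.** That test changes two things, so they were separated (LOCF, 5,000 trials, SE about 0.25; settings in the order 2.5/1.5, 2/1.5, 2.5/2).

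| Errors | Stratifying alone | Percentage to absolute change | Sum |
|---|---|---|---|
| Left-skewed | +0.8/+1.5/+1.0 | +2.1/+2.5/+1.3 | +2.9/+4.0/+2.3 |
| t, 4 df | +0.2/+1.1/+0.5 | +1.5/+1.9/+0.5 | +1.7/+3.0/+1.0 |

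With normal errors, stratifying alone gives +1.2/+2.0/+1.7, and dropping the percentage about 0.5-2. Over all simulations run, stratifying alone is worth about 0-3 points and the change of scale about 0.5-4.5. The total is roughly 1-8, with the upper end coming from skewed errors and complete follow-up. Rank ANCOVA with non-normal errors ranges from −0.7 to +3.7 under LOCF and from −0.2 to +5.4 with complete data.

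**Step 5: slope near 1** (3/0.7, slope 0.94, effect 0.46). Complete data: planned 44.6%, van Elteren 46.7%, so +2.1. Mann-Whitney on absolute change also gives 46.7%, so stratifying adds nothing there. With LOCF the total gain is +0.9.

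**Step 6: MCID proportions.** With simulated rates of 24% and 42% and 40 per arm, the unstratified 95% half-width is 1.96 × √(0.24×0.76/40 + 0.42×0.58/40) = 1.96 × 0.103 = 20 percentage points. Stratified, it is about 18-20 over the settings in Step 3.

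**The case against.** The strongest reply is that nothing here is wrong, only improvable: the comparison is randomised, the omission does not inflate error, every magnitude is assumed, and the plan is written in the past tense. That stands, and it limits the point to a recommendation.

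Several narrower objections also stand.

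- A reader might infer that the whole gain comes from using the strata. Step 4 shows otherwise. With non-normal errors, which is what the plan asserts, dropping the percentage contributes more than stratifying in five of six settings and the same, to one decimal, in the sixth.
- A reader might infer that the planned test is conservative without condition. That needs balance within strata, and the Procedure section states only a 1:1 ratio. With simple randomisation the test is close to nominal.
- Rank ANCOVA can lose a little power with non-normal errors, and the gains of 5-8 points seen for ordinary ANCOVA need normal errors.
- LOCF was simulated only as post equal to baseline. At follow-up, someone missing only that visit carries the post score forward, so the power figures cover the post-intervention visit only.
- The MCID interval is a reporting matter, separate from the primary test. An approximate one can be built from the two percentages and the arm sizes. The plan also promises descriptive statistics at all three assessments.

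Non-normality is not a defence of the planned test, however. Van Elteren is also rank-based and gained power in every skewed and heavy-tailed setting run.

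**Conclusion.** The point holds as lost efficiency. The plan stratifies on MoCA and then tests MoCA without the stratum or a baseline covariate. Under the stated assumptions (N = 80, 1-point effect, slope about 0.6-0.8, post-intervention visit), a van Elteren test on absolute change recovers roughly 1-8 points of power, of which stratifying accounts for about 0-3. Near slope 1 the total is near zero to 2 points. In the N = 68 simulations the stratum explained about 3-13% of the rank variance, equivalent to about 2-9 of 68 participants (68 × 0.035 = 2.4; 68 × 0.13 = 8.8).

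Two stronger readings are not supported. One is that the planned test is biased or anti-conservative because it ignores the strata: it stayed below 5% in every setting tabulated, and a further N = 80 check with simple randomisation gave about 5.0%. The other is that the primary analysis has been shown valid as a whole. Only the omission of strata and baseline was examined; LOCF and delivery in groups of 4-6 are separate matters. For example, with groups of 5 in both arms and an assumed ICC of 0.01-0.05 (design effect 1 + 4 × ICC = 1.04-1.20), ignoring clustering alone would put size at about 0.055-0.074.

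**What to change.** - Test MoCA change in points, at post and at follow-up, with a van Elteren test stratified by 19-22/23-25. This keeps the plan's rank-based approach. Rank ANCOVA of post MoCA on baseline is an acceptable alternative, but its gain with non-normal errors is less certain.
- Report the baseline-adjusted between-group difference in MoCA points with a 95% CI, for example ANCOVA with a bootstrap interval. In the Step 3 settings the ANCOVA half-width was 0.80-1.13 points. Do not judge this mean difference against 1.22 points: "MCID is defined as the smallest change in scores perceived by the patient as beneficial", so it is a threshold for an individual's change, and the plan borrows it from stroke rehabilitation.
- As a minor reporting addition, give the between-group difference in the proportion reaching the MCID with a 95% CI.
- State whether allocation was blocked within strata.

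If the analysis is complete, present the new analyses as labelled post hoc sensitivity analyses beside the planned Mann-Whitney test, not in its place. The cost is SAP wording and a re-run, with no new data.
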